As part of the clinic-based testing for the study, participants will be asked to (1) complete online surveys with validated patient-reported questionnaires about their pain and function. The single-session of education and instruction (load modification vs standard exercise) will be performed by a licensed physical therapist immediately after the testing procedures are complete. Participants will undergo the same clinic-based testing protocol at the 4-week follow-up prior to their visit with the physician in the Jameson Crane Sports Medicine Institute at OSUWMC. For 4-weeks following the initial evaluation and clinic-based testing, participants will be asked to complete weekly online/telephone surveys to document their hip pain and function as well as their compliance with the prescribed home exercise program. Key variables of interest (Table 2) include the Global Rating of Change scale¹⁸ and the Numeric Pain Rating Scale^{18,33,34}. The other secondary variables of interest will help us more completely assess the effect of the proposed program hip function questionnaires, overall function,³⁵⁻³⁷ activity level,³⁸ and self-efficacy.³⁹

Table 2. Variables of Interest

[figure not shown]
Primary VOIs	Secondary VOIs
Global Rating of Change (GROC) (Mellor 2016)	Frontal plane kinematics of the trunk, pelvis, hip, and knee during a single leg squat
Numeric Pain Rating Scale (NPRS) (Farrar 2010, Fearon 2017, Mellor 2016)	Victorian Institute of Sport Assessment for Greater trochanteric pain syndrome (VISA-G) (Fearon 2014)
	Pain Self-Efficacy Questionnaire (PSEQ) (Nicholas MK 2007)
	Patient Acceptable Symptomatic State question (PASS) (Levy 2016, Chalal 2015)
	Patient Reported Outcomes Measurement Information System (PROMIS) Bank v2.0 Physical Function
	Tegner Activity Level Scale (TALS) (Mohtadi 2012)

A. Sample size estimation:

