B. Randomization, concealed allocation, and blinding: A randomization list will be generated and secured with the study biostatistician prior to the start of the study. It will contain study-specific unique identifiers (ie. GTPS1, GTPS2, etc) and a binary code for treatment group (ie. 0 or 1). A copy of this list will be provided to the Sports Medicine Clinical Research Manager who provides administrative support to all clinical trials in the Sports Medicine Institute. The Manager will determine the group assignment (e.g. 0 = LM, 1 = SE) independent of the biostatistician and the PI. The PI will put together 30 concealed envelopes for each treatment group that contain the group assignment and the appropriate exercise program instructions (SE vs LM) and provide these to the

Manager. The Manager will then label, seal, and place them in a drawer in the physician. The Manager will not be involved in the recruitment, testing, or analysis involved with this trial. She will be the only person with the UID, randomization order, and treatment allocation data all in one place. These data will be stored under lock and key in the private office of the Manager, and in a password-protected file, accessible only to the Manager.

After consent, participants will proceed with testing by a blinded tester. Randomization and group allocation will occur immediately following testing. After testing, the tester will inform the treating physical therapist of group (e.g. 0 vs 1). The drawer with the concealed/sealed envelopes will be accessible to the treating physical therapist and the physicians. The treating physical therapist will select the next available envelope from the appropriate group (0 vs 1) and proceed with the assigned treatment; only when she or he breaks the envelope seal will she or he know the group assignment (LM vs SE).

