C. Blinding: Investigators involved in the participant testing and statistical analysis of the outcome variables of interest will be blinded to group allocation. The treating physicians, physical therapist interventionists and patients cannot feasibly be blinded to treatment arm. Participants will not be informed of the study hypotheses and unblinded investigators will not share group allocation information with the blinded investigators. All references to group assignment in other research documentation (ie. REDCap™, video data collection form) will be coded (ie. '0' and '1') to maintain blinding. One trained tester will consent and perform baseline and 4-week follow-up testing. At the 4-week follow-up, the physician will re-evaluate the participant with the clinical diagnostic criteria and discuss their compliance and response to the home exercise program. As is consistent with standard of care, the physician and patient will determine the next course of treatment. The treatment plan will be entered using custom coding (ie. 'smart phrases') to allow discrete data to be queried. Statistical analysis will be performed by the blinded study biostatistician with input from the PI (see Statistical Analysis Plan). After the physician finishes his/her visit with the participant, the tester will proceed with the 4-week follow-up testing and will remind the participant she or he is blinded to treatment and cannot receive any information about the group to which they have been assigned.

D. Clinic-based testing: Baseline testing and treatment will occur in the clinic, immediately following the physician evaluation and confirmation of GTPS diagnosis, for all patients who consent to participate in the study. The clinic-based testing sessions will occur at baseline (immediately after randomization) and at the 4-week clinical visit by a blinded tester. These testing sessions will take about 10 minutes for the questionnaires. Clinic-based testing will include patient-reported questionnaires using Research Electronic Data Capture (REDCap™) survey. REDCap™ is a secure, web-based application that supports data capture, auditing, and exporting⁴⁰ to gather baseline data with regard to their pain and level of function⁴¹ and is hosted at The Ohio State University. Participants will be given the option to complete the survey on either our research handheld tablet (iPad) or laptop or desktop provided by the researcher.

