E. Intervention: The single physical therapy educational and instructional session will occur at baseline, immediately following the clinic-based testing. This session will be administered by the unblinded physical therapist interventionists who is trained to administer these protocols. **Participants will receive either (1) standard exercise education and instruction (SE) or (2) load modification education and instruction (LM), based on their treatment group randomization.** Standard exercise education includes exercises currently prescribed by physical therapists, like stretching and strengthening activities. Participants randomized to the load modification group will undergo approximately 5 additional minutes of education and instruction about their posture and movement modifications and will also be provided an information sheet with text and pictures (see Appendix: Supplements). Both groups will be instructed to perform the home exercise program once per day, performing Level 1 activities for the first two weeks and Level 2 activities for the last two weeks. (see Appendix. Supplements - Home exercise programs for both groups). Both groups will receive handouts with pictures and detailed instructions for each of their exercises.

a. Home exercise program (HEP): Both protocols were modelled after current literature for a standard lower extremity exercise program for GTPS and a load modification program. The load modification program from Mellor and colleagues (2016) was further adapted to include exercise dosage shown to be effective in

patellar tendinopathy trials.^{29,30} The HEP will be instructed and guided by the physical therapist, in combination with practice by the patient, and demonstration by the therapist, if needed. It is expected that program instruction will take about 15-20 minutes in both groups and that the home programs themselves will take between 15-20 minutes. The physical therapist will provide standardized cueing to optimize technique. Participants will be provided opportunities to ask questions during the session and provided a written home program with text and pictures for the patient to follow. These instructions, including the pictures will be made available online through REDCap™, along with instructional videos to provide the participant an additional resource to clarify technique.

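### Baseline testing comes before randomisation in Section B but after it in Section D, so the plan does not guarantee a pre-randomisation NPRS

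*Combined protocol and SAP*

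**What the plan says.** Section B (Randomization, concealed allocation, and blinding) gives a stepwise order. First, "After consent, participants will proceed with testing by a blinded tester". Then, "Randomization and group allocation will occur immediately following testing". Disclosure follows: "After testing, the tester will inform the treating physical therapist of group (e.g. 0 vs 1"). The therapist takes the next envelope for that code, and "only when she or he breaks the envelope seal will she or he know the group assignment (LM vs SE").

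Section D (Clinic-based testing) gives the opposite order: "The clinic-based testing sessions will occur at baseline (immediately after randomization) and at the 4-week clinical visit by a blinded tester". It describes this testing as questionnaires completed in REDCap "to gather baseline data with regard to their pain and level of function".

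Section E (Intervention) adds: "The single physical therapy educational and instructional session will occur at baseline, immediately following the clinic-based testing".

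The overview text before Table 2 says that the key variables "include the Global Rating of Change scale¹⁸ and the Numeric Pain Rating Scale". The Statistical analysis plan defines success as either a GROC rating of at least moderately better or an NPRS fall of 2 points or more. Section C (Blinding) has one trained tester obtain consent and do both the baseline and the 4-week testing, and says that participants cannot be blinded to their arm. The Recruitment and Informed Consent section requires enrolment on the day of the physician visit, but lets the REDCap questionnaires be completed later by emailed link or by phone.

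**The concern.** A baseline value is protected from the influence of assignment when it is recorded before the participant is randomised. Section B provides that order and Section D gives it up. The two sections describe the same session, so staff must choose one, and nothing in the plan tells them which.

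What is at stake is the reference value for one of the two routes to primary success. The tester handles the group code as well as the baseline measurements. If randomisation comes first, the tester may already have the code while baseline is being taken. The code is meant to be uninformative, but it appears to have one fixed meaning throughout the trial, and the same tester meets unblinded participants again at week 4. A single disclosure at a follow-up visit could let the tester decode later assignments. Recording baseline before the code is available closes that path.

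**Working it through.** This is a question of order, so the sections are compared directly.

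**1. The two sequences**

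| Step | Section B | Section D |
|---|---|---|
| 1 | Consent | Consent |
| 2 | Baseline testing | Randomisation |
| 3 | Randomisation and allocation | Baseline testing |
| 4 | Code to therapist, envelope opened, treatment | Not restated; Section B's steps still apply |

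Steps 2 and 3 are reversed.

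**2. Does other text settle it?** No. Section E and the overview both place the treatment session after testing, which fits either sequence. The opening sentence of Section D ties baseline testing to the physician evaluation and does not mention randomisation.

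**3. What differs between the sequences?** The randomisation list is generated before the study starts in both cases, so the existence of a list is not the difference. Section B's disclosure steps also stand in both cases: the therapist receives the code after testing and learns the arm on breaking the seal. What changes is whether this participant's assignment has been made, and could be in the tester's hands, while baseline is recorded. The plan says when the tester passes the code on. It does not say when the tester receives it.

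**4. Which outcome depends on a baseline value?** The GROC asks directly about change and needs no baseline score. The NPRS route needs a reference. The plan does not name the assessment that serves as reference; baseline is the natural reading and is assumed here.

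**5. Does correcting Section D suffice?** No. Under the Recruitment and Informed Consent section, a participant may enrol, be randomised and be treated that day, yet complete the baseline questionnaires later. An NPRS deferred in this way would be recorded after assignment and treatment by someone who knows the arm, even under Section B's order.

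**6. Do any stated figures depend on the order?** The sample size section gives 20% and 50% success, one-sided type I error 0.1, power 80% and 1:1 allocation. With pooled variance and no continuity correction:

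n per group = [1.2816 × √(2 × 0.35 × 0.65) + 0.8416 × √(0.20 × 0.80 + 0.50 × 0.50)]² / 0.30²
= [1.2816 × 0.6745 + 0.8416 × 0.6403]² / 0.09
= 1.4034² / 0.09 = 21.9, rounded up to 22, or 44 in total.

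Allowing for 30% attrition, 44 / 0.70 = 62.9, or 63; the stated 64 is 32 per group. No input involves the order of testing and randomisation, so the correction changes none of these figures.

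**7. Can the bias be sized?** No. That would need the shift in baseline NPRS by arm, the distribution of NPRS change, and the share of participants who succeed on the NPRS but not on the GROC. The documents give none of these.

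**The case against.** The strongest reply is that this is a drafting slip with little consequence. Section B is the section devoted to randomisation and sets out the sequence step by step; the contrary text in Section D is one parenthesis. The list exists before the study under either order. For testing done in clinic, a participant rating pain has not been treated, and on the plan's own steps has not been told the arm. An early leak to the therapist would require someone to depart from Section B by opening a sealed envelope too soon.

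Most of this stands, and it limits the concern to a possible bias. It does not remove the contradiction: Section D is the section on conducting the baseline session, and staff who follow it literally would randomise first. Nor does it cover the tester, whose receipt of the code has no stated time.

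A reader might infer more than the documents support:

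- **That post-randomisation baselines would certainly be contaminated.** The disclosure steps in Section B argue against this.
- **That the effect can be quantified from the planning rates of 20% and 50%.** Those rates describe overall success by either route. Applying them to the NPRS route alone, with an invented baseline shift, would not estimate the effect on the primary endpoint.
- **That the kinematic change scores are equally exposed.** Section D describes only questionnaires and does not place video testing in this session.
- **That the retention denominator changes.** The plan does not define one by test order. The only affected participant would be someone who left during a session of about 10 minutes.
- **That different centres would follow different sections.** Recruitment is from one institute's clinics, with one tester.

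**Conclusion.** The plan is wrong as written on the order of baseline testing and randomisation. Sections B and D contradict each other and no other text resolves the conflict. Following Section D would give up a pre-randomisation baseline for the NPRS route to primary success and could leave the single tester holding the group code while baseline is taken.

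Confidence in the contradiction is high. The consequence is a possible bias of unknown size, confined to participants whose success turns on the NPRS. This rests on two assumptions: that baseline is the reference for the NPRS fall, and that the code keeps one meaning throughout the trial, as the example in Section B suggests. If nobody involved in baseline testing knows or infers the arm, including the participant, the order introduces no bias. The correction is still worth making because it is cheap and protects a component of the primary endpoint.

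**What to change.** 1. In Section D, replace the parenthesis attached to the baseline session with: *after consent and before randomization*. This brings it into line with Section B.
2. In Section B, add that the tester obtains the 0/1 code only after the participant's baseline NPRS has been recorded.
3. In the Recruitment and Informed Consent section, add that the single-item NPRS is recorded at the enrolment visit before the code is released, while the other questionnaires may still be completed later by link or phone.

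The third change is needed for the second to work. Holding the code until every baseline questionnaire was complete would conflict with the deferral option, because a participant using it could not be randomised and treated on the day of enrolment. Limiting the rule to the NPRS keeps same-day treatment and most of the flexibility.

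The cost is that one brief item can no longer be deferred. No extra staff or visits are needed, and the sample size is unaffected.

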To inform our sample size estimation for this feasibility randomized controlled trial, we used the available literature which reported a 7% treatment success rate at 4-weeks following a single, standard exercise session (ie. non-load modifying)⁶ and the hypothesized 70% treatment success rate following an 8-week to a supervised load modification program.¹⁸ Conservatively, we estimated that the standard exercise (SE) group and load modification (LM) group would have a 20% and 50% success rate, respectively. **With one-side type I error=0.1, power=80%, and allocation ratio is 1:1, we will need 22 participants in each group (total N=44). We will recruit 64 individuals with GTPS to account for up to 30% attrition over the course of the study due to drop-out.** To fully recruit the study after proper regulatory approval is in place and staff are trained, we anticipate a 15-month recruitment time-frame for the 60 participants. This factors in a recruitment rate of 5 participants per month (see Letters of Support/Collaboration), from an eligible 10 (minimum 50% recruitment rate).

Recruitment and Informed Consent (Figure 1): Prior to enrollment, written informed consent will be obtained from all potential participants after information about the purpose, methods, and demands of the study is provided both verbally and in writing (via the consent documentation) to the participant. The participants for this trial will be recruited from the Jameson Crane Sports Medicine Institute physician clinics at OSUWMC during their on-site medical visit. Once the treating physician confirms GTPS diagnosis through our standardized and validated clinical examination process (Table 1, Inclusion Criteria),^{18,31} the study recruiter will then discuss the study opportunity with the patient and proceed with the consenting process when appropriate.

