Post collection data storage and analysis: A blinded study team member will be responsible for 2D video quality control and creating trial clips for subsequent analysis. Video analysis will begin after the last participant completes their 4-week follow-up. These data will be used to determine measurement variability (intraclass correlation coefficients, standard error of the measurement, and minimal detectable change values) and provide information with regard to changes in movement patterns as a result of program participation. Frontal plane kinematics (peaks and excursions) of the trunk, pelvis, hip, and knee will be calculated (Kinovea version 0.8.15) for each task. Analysis will include the double and single leg static starting postures and peak frontal plane motion (as identified using the joint position tracking function). Lines will be drawn through the long axes of the bones for the shank and thigh, through the ASIS for the pelvis, and from the sternum to the midpoint of the ASIS line (Figure 2). Horizontal and vertical 'lab axes' will be applied to the image to allow calculations relative to pure horizontal (ie. pelvic drop) and pure vertical (ie. trunk lean). Angles will also be calculated with respect to the proximal segment.

Statistical analysis plan:

An intention to treat approach is planned for all analyses, using all participants who were randomized who have available data at 4 week follow-up. Where appropriate, normality will be assessed and non-parametric approaches will be used when assumptions are violated. Demographics and clinical characteristics (ie. age, sex distribution, BMI, baseline pain scores, etc) will be summarized for SE and LM groups, respectively, and compared between the groups using two-sample t-test for continuous outcomes or Fisher's exact test for discrete outcomes.

To evaluate the effect of treatment group allocation on dichotomized treatment success (Aim 1, Hypothesis 1), defined as either: 1) at least 'moderately better' on the Global Rating of Change scale or 2) ≥ 2 point decrease on the Numeric Pain Rating Scale, we will use Fisher's exact test to compare the success rate between SE and LM group. Frontal plane kinematics are a secondary variable of interest (Aim 1, Hypothesis 2). With the available 2D data set, we will compare change scores between groups using independent t-tests and/or effect sizes. These data may serve as preliminary data for future grant applications.

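### Minor improvement: the kinematic change-score comparison does not use the baseline value as a covariate, and a baseline-adjusted regression would usually be more precise

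*Combined protocol and SAP*

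**What the plan says.** Table 2 lists "Frontal plane kinematics of the trunk, pelvis, hip, and knee during a single leg squat" as a secondary variable, and the Statistical analysis plan ties it to Aim 1, Hypothesis 2. The analysis is given in one sentence, which opens "With the available 2D data set" and continues "we will compare change scores between groups using independent t-tests and/or effect sizes". The next sentence gives the purpose: "These data may serve as preliminary data for future grant applications". A general sentence in the same section adds that "non-parametric approaches will be used when assumptions are violated". That sentence concerns distributional assumptions and not adjustment. Nowhere else do the documents give a kinematic model that includes the baseline value.

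**The concern.** A change-score comparison fixes the slope of the 4-week value on the baseline value at 1. A regression on group and baseline estimates that slope. If the true slope is well below 1, the change score carries avoidable noise from the baseline measurement, and the estimated group difference is less precise than the same videos allow.

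What is at stake is limited. The kinematic results are meant as preliminary data, so the size and precision of the estimate are what the analysis delivers. The plan promises exact confidence intervals for retention and compliance but none for kinematics. The primary comparison, the sample size and the feasibility aims do not depend on this choice.

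**Working it through.** **The plan's own figure.** The only calculated sample size is for the binary endpoint (A. Sample size estimation): success rates of 20% and 50%, one-sided 0.10, 80% power. The pooled normal formula gives [1.2816 × √(2 × 0.35 × 0.65) + 0.8416 × √(0.16 + 0.25)]² / 0.30² = 1.969 / 0.09 = 21.9, so 22 per arm, as stated. No sample size or power is stated for kinematics. I use 22 per arm below for illustration only.

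**Inputs that the documents do not give.** The correlation r between baseline and 4-week values, the ratio k of 4-week SD to baseline SD, and the number n per arm with paired videos are all assumptions, shown as ranges.

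**Formulas** (equal arms; the same slope and SDs in both arms; bivariate normal; baseline SD s):

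- Change-score difference: variance = (2/n)(1 + k² − 2rk)s².
- Baseline-adjusted difference: variance = (2/n)k²(1 − r²)s² × B, where B = 1 + 1/(2n − 4) is the cost of estimating the slope.
- Ratio, adjusted to change score = B × [1 − (1 − rk)²/(1 + k² − 2rk)]. Below 1 favours adjustment.

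**Example.** With n = 22, k = 1, r = 0.5: B = 1 + 1/40 = 1.025, and the ratio is 1.025 × 0.75/1.00 = 0.769, a variance about 23% lower. At r = 0.7 it is 1.025 × 0.51/0.60 = 0.871. At r = 0.9 it is 1.025 × 0.19/0.20 = 0.974.

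| n per arm | k | r = 0.3 | 0.5 | 0.7 | 0.8 | 0.9 |
|---|---|---|---|---|---|---|
| 22 | 1 | 0.67 | 0.77 | 0.87 | 0.92 | 0.97 |
| 10 | 1 | 0.69 | 0.80 | 0.90 | 0.96 | 1.01 |
| 5 | 1 | 0.76 | 0.88 | 0.99 | 1.05 | 1.11 |
| 22 | 1.25 | 0.80 | 0.92 | 1.005 | 1.025 | 0.97 |
| 10 | 1.25 | 0.83 | 0.95 | 1.04 | 1.06 | 1.01 |
| 22 | 0.75 | 0.47 | 0.53 | 0.57 | 0.57 | 0.52 |

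**Confidence interval width.** The width ratio is √(variance ratio) × t(0.975, 2n − 3)/t(0.975, 2n − 2). At 22 per arm and k = 1, the adjusted 95% CI is about 12%, 7% and 1% narrower at r = 0.5, 0.7 and 0.9.

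**When adjustment loses.** The bracket in the ratio cannot exceed 1, so under these assumptions the ratio is at most B, reached when the slope rk equals 1. That gives 1.025, 1.0625 and 1.167 at 22, 10 and 5 per arm, with the CI 1.3%, 3.5% and 10.8% wider. With equal SDs a loss needs r above 0.95, 0.88 and 0.71 respectively. If the 4-week SD is 1.25 times the baseline SD, a loss occurs at more ordinary correlations: about 0.69 to 0.88 at 22 per arm.

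**Simulation.** Simulated ratios match the formula (n = 22, k = 1: 0.768, 0.873 and 0.970 at r = 0.5, 0.7 and 0.9), and both estimators are unbiased. If the arms are unequal and the slopes differ between them, the bound B no longer applies. With baseline SD 1 and residual SD 0.5, the ratios were about 1.06 (arms 26 and 18, slopes 1.3 and 0.7), 1.12 (arms 12 and 8, slopes 0.6 and 1.2) and 1.26 (arms 14 and 6, slopes 0.6 and 1.2). These slopes are assumed, to show that larger losses can occur.

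**The case against.** The strongest objection is that this is a preference and not a flaw. The planned test is valid, the outcome is secondary and preliminary, and the benefit cannot be established because r, the SDs and the paired n are all absent. That stands, and it is why the point is minor and the figures are conditional.

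The usable n may also be small. D. Clinic-based testing says "These testing sessions will take about 10 minutes for the questionnaires" and allots no time to filming. With about 5 per arm and equal SDs there is no useful gain at r = 0.7 and a loss at 0.8 and 0.9. This is a hint only, since G. Data management still describes video collection.

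A further objection is that change scores have a use here. The section on post-collection analysis derives the standard error of measurement and minimal detectable change from the same videos, and those are read in change units. This also stands, so mean change should be kept beside the adjusted comparison.

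A reader might infer three stronger claims:

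- That the change-score test is biased or wrong. Under randomisation it is neither.
- That adjustment always gains. The table shows cases where it does not.
- That the loss is capped whatever the correlation and SDs. The cap needs equal arms and a common slope and SD. The plan analyses available data, so the arms may be unequal, and it compares programmes that may alter movement differently, so the slopes may differ.

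**Conclusion.** The point holds as a minor, optional improvement. Every participant in the planned kinematic comparison already has the covariate, and no part of the plan uses it as one. With equal arms, a common slope, equal SDs and an illustrative 22 per arm, adjustment lowers the variance by about 23%, 13% and 3% at r = 0.5, 0.7 and 0.9. With equal arms and a common slope and SD, the possible loss is at most 2.5%, 6.3% and 16.7% of variance at 22, 10 and 5 per arm. It can exceed those figures when arms are unequal and slopes differ. The balance usually favours adjustment, but the documents do not allow its size, or even its direction, to be fixed for this trial.

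**What to change.** The Post collection section says "Video analysis will begin after the last participant completes their 4-week follow-up", so the model can be settled before kinematic results exist. Before that point, state in the Statistical analysis plan:

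- For each kinematic variable, the between-group comparison is the group coefficient from a linear regression of the 4-week value on treatment group and the baseline value of that variable. It is reported as an adjusted mean difference with 95% CI and a standardised effect size.
- If normality is violated, one fallback named in advance applies, such as a permutation test of the group effect in the same model. A choice left open between methods would depend on the data, and a rank-based model would not give the adjusted mean difference.
- Mean change by group is kept as a descriptive summary, to be read against the minimal detectable change.
- If only a handful per arm have paired videos, the estimate is treated as descriptive.

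Fisher's exact test of treatment success stays primary. The cost is a few lines of text and one degree of freedom per model, with the possible small loss of precision given above. No new data are needed.
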